3.2. Study Definitions and Derived Variables

For individual subjects, fold rise will be calculated as the ratio of: $\frac{\text{post-vaccination titer}}{\text{pre-vaccination titer}}$, where pre-vaccination value is the result obtained at Day 1 prior to the priming dose. However, for assay results against 2019/2020 QIV strains, pre-vaccination titer is the result obtained at Day 90.

HAI Seroconversion is defined as either a pre-vaccination titer $<1:10$ and a post-vaccination titer $\geq 1:40$ **or** a pre-vaccination titer $\geq 1:10$ and a minimum four-fold rise in post-vaccination antibody titer [1].

NAI seroconversion is defined as ≥ 4 -fold rise in post vaccination antibody titers against the NA antigens in the 2018/2019 QIV.

Neut Seroconversion is defined as either a pre-vaccination titer $<1:10$ and a post-vaccination titer $\geq 1:40$ **or** a pre-vaccination titer $\geq 1:10$ and a minimum four-fold rise in post-vaccination antibody titer.

Seronegative baseline status is defined as pre-vaccination antibody titer of $\leq 1:10$.

Seropositive baseline status is defined as pre-vaccination antibody titer of $>1:10$.

For HAI and Neut assays, Seroprotection is defined as titer ≥ 40 .

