### **5.1.3 Exclusion Criteria for Second Study Vaccination**

All study participants will be expected to receive the second study vaccination except under the circumstances listed below. The second study vaccination will not be administered to a subject if any of the following criteria are met:

- Meets the contraindication on the package insert to receipt of licensed influenza vaccine.
- As deemed necessary by the site principal investigator or appropriate sub-investigator for noncompliance or other reasons.
- Subject refusal of further study vaccination.
- Withdrawal of consent.
- Subject is lost to follow-up.
- Termination of this trial.
- New information becomes available that makes further participation unsafe.

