#### **8.2.5 Visit 06, Day 90, Clinic Visit**

##### **(Window: Day 90 +/- 14d)**

- Interim medical history, including an assessment for new medical conditions, stability of chronic diseases and symptoms suggestive of AESIs (including Protocol Specified AESIs, MAAEs, NOCMCs and PIMMCs), will be obtained by interview of subjects and any changes since the previous clinic visit will be noted.
- Receipt of any non-study influenza vaccines will be recorded on the appropriate DCF.

- SAEs, AESIs (including Protocol Specified AESIs, MAAEs, NOCMCs and PIMMCs) will be recorded on the appropriate DCF.
- A targeted physical examination performed prior to study vaccination, including an assessment for signs suggestive of AESIs (including Protocol Specified AESIs, MAAEs, NOCMCs and PIMMCs), may be performed, if indicated based on review of interim medical history, by a study clinician licensed to make medical diagnoses and listed on the Form FDA 1572 as the site PI or sub-investigator .
- Approximately 20 mL of venous blood will be collected immediately prior to study vaccination for serological assays.
- Approximately 48 mL of venous blood will be collected immediately prior to study vaccination for immunological assays.
- Subjects will then receive one 0.5 mL dose of 2019-2020 Fluzone or Flublok QIV study vaccine via a single IM injection into the deltoid muscle of the subject's preferred arm. Subjects who received 2018-2019 Fluzone QIV will receive 2019-2020 Fluzone QIV. Subjects who received 2018-2019 Flublok QIV will receive 2019-2020 Flublok QIV. The site of injection (right or left arm) and time of study vaccine administration to the subject will be recorded on the appropriate DCF. Any SAE's will be recorded on the appropriate DCF prior to discharge.

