#### **8.2.6 Visit 07, Day 118, Clinic Visit**

##### **(Window: Day 118 +/- 3d)**

- Interim medical history, including an assessment for new medical conditions, stability of chronic diseases and symptoms suggestive of AESIs (including Protocol Specified AESIs, MAAEs, NOCMCs and PIMMCs), will be obtained by interview of subjects and any changes since the previous clinic visit will be noted.
- Receipt of any non-study influenza vaccines will be recorded on the appropriate DCF.
- SAEs, AESIs (including Protocol Specified AESIs, MAAEs, NOCMCs and PIMMCs) will be recorded on the appropriate DCF.
- A targeted physical examination, including an assessment for signs suggestive of AESIs (including Protocol Specified AESIs, MAAEs, NOCMCs and PIMMCs), may be performed, if indicated based on review of interim medical history, by a study clinician

licensed to make medical diagnoses and listed on the Form FDA 1572 as the site PI or sub-investigator.

- Approximately 20 mL of venous blood will be collected for serological assays.

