## **8.5      **Unscheduled Visit (if needed)****

An Unscheduled Visit may occur at any time during this trial. Any of the following activities may be performed:

- Interim medical history, including an assessment for new medical conditions, stability of chronic diseases and symptoms suggestive of AESIs (including Protocol Specified AESIs, MAAEs, NOCMCs and PIMMCs) will be obtained by interview of subjects and any changes since the previous clinic visit or phone call will be noted (if indicated).
- All concomitant medications will be recorded on the appropriate DCF (if within 28 days after first study vaccination). Receipt of any non-study influenza vaccines will also be recorded on the appropriate DCF (if within 365 days after first study vaccination).
- All AE/SAEs will be recorded on the appropriate DCF. Unsolicited AEs (if occurs within 28 days of the first study vaccination). SAEs and AESIs (including Protocol Specified AESIs, MAAEs, NOCMCs and PIMMCs) that have occurred since the previous clinic visit will be solicited (if within 365 days after first study vaccination).

- Memory Aid information will be reviewed with subjects (if within 7 days after the first study vaccination).
- Vital signs, including oral temperature, pulse and BP, may be obtained if indicated. Subjects must not eat or drink anything hot or cold, or smoke within 10 minutes prior to taking oral temperature.
- A targeted physical examination, including an assessment for signs suggestive of AESIs (including Protocol Specified AESIs, MAAEs, NOCMCs and PIMMCs), may be performed, if indicated based on review of interim medical history, by a study clinician licensed to make medical diagnoses and listed on the Form FDA 1572 as the site PI or sub-investigator.
- The study vaccination site will be examined (if within 7 days after study vaccination).
- Post administration reactogenicity assessment will be performed (if within 7 days after the first study vaccination).
- Site investigators have the discretion of administering 2019/2020 Fluzone or Flublok QIV earlier than the Day 90 window (i.e. earlier than Day 76) if 10% or more of surveillance samples in the CDC geographic region surrounding the local site test positive for influenza.
- Approximately 6 mL of venous blood will be collected for clinical safety labs (WBC, Hgb, PLT, ALT, T. Bili, AST, GGT, ALP serum lipase and amylase and Cr) to be performed by the Central Clinical Laboratory (if indicated).

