Analysis Populations	Reason Subjects Excluded	Group 1 Fluzone (N=X)		Group 2 Fluzone + AF03 (N=X)		Group 3 Fluzone + Advax- CpG (N=X)		Group 4 Flublok (N=X)		Group 5 Flublok + AF03 (N=X)		Group 6 Flublok + Advax- CpG (N=X)		All Subjects (N=X)	
		n	%	n	%	n	%	n	%	n	%	n	%	n	%
	No Baseline Results Available														
	No Day 90 Result Reported by Lab														
	Lost to Follow-up Before Day 90														
	Receipt of Non-Study Vaccination														
	Receipt of Immunosuppressive medication														
	Day 90 Visit Out of Window														
Per Protocol, Day 118	Any Reason														
	Study Vaccination 1 Not Received														
	No Baseline Results Available														
	No Day 118 Result Reported by Lab														
	Lost to Follow-up Before Day 118														
	Receipt of Non-Study Vaccination														
	Receipt of Immunosuppressive medication														
	Day 118 Visit Out of Window														
Per Protocol, Day 180	Any Reason														
	Study Vaccination 1 Not Received														
	No Baseline Results Available														

Analysis Populations	Reason Subjects Excluded	Group 1 Fluzone (N=X)		Group 2 Fluzone + AF03 (N=X)		Group 3 Fluzone + Advax- CpG (N=X)		Group 4 Flublok (N=X)		Group 5 Flublok + AF03 (N=X)		Group 6 Flublok + Advax- CpG (N=X)		All Subjects (N=X)	
		n	%	n	%	n	%	n	%	n	%	n	%	n	%
	No Day 180 Result Reported by Lab														
	Lost to Follow-up Before Day 180														
	Receipt of Non-Study Vaccination														
	Receipt of Immunosuppressive medication														
	Day 180 Visit Out of Window														
Per Protocol, Day 365	Any Reason														
	Study Vaccination 1 Not Received														
	No Baseline Results Available														
	No Day 365 Result Reported by Lab														
	Lost to Follow-up Before Day 365														
	Receipt of Non-Study Vaccination														
	Receipt of Immunosuppressive medication														
	Day 365 Visit Out of Window														

N = Number of subjects enrolled.

Table 13: Subject Disposition by Study Arm, All Enrolled Subjects*

Subject Disposition	Group 1 Fluzone (N=X)		Group 2 Fluzone + AF03 (N=X)		Group 3 Fluzone + Advax- CpG (N=X)		Group 4 Flublok (N=X)		Group 5 Flublok + AF03 (N=X)		Group 6 Flublok + Advax- CpG (N=X)		All Subjects (N=X)	
	n	%	n	%	n	%	n	%	n	%	n	%	n	%
Screened	x	--	x	--	x	--	x	--	x	--	x	--	x	--
Enrolled/Randomized	x	100	x	100	x	100	x	100	x	100	x	100	x	100
Received Vaccination 1	x	xx	x	xx	x	xx	x	xx	x	xx	x	xx	x	xx

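### The baseline for responses to the 2019/2020 strains is fixed at Day 90 whatever the actual date of dose 2, although dose 2 may be given before Day 76 or not at all

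*SAP*

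**What the plan says.** **Baseline rule.** SAP 3.2 takes Day 1 as the pre-vaccination titer in general, then makes an exception: "However, for assay results against 2019/2020 QIV strains, pre-vaccination titer is the result obtained at Day 90". The same pre-vaccination titer feeds the fold rise, the seroconversion rule (for subjects at 1:10 or above, "a minimum four-fold rise in post-vaccination antibody titer") and baseline serostatus.

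**Intended order.** At Visit 06 (protocol 8.2.5, "Window: Day 90 +/- 14d"), "Approximately 20 mL of venous blood will be collected immediately prior to study vaccination for serological assays", and dose 2 follows. Visit 07 (protocol 8.2.6) is set by study day: "Window: Day 118 +/- 3d". The secondary outcome measures describe Day 118 as 28 days after the 2019/2020 vaccine.

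**Permitted departures.** Protocol 8.5: "Site investigators have the discretion of administering 2019/2020 Fluzone or Flublok QIV earlier than the Day 90 window", if regional influenza positivity reaches 10%. SAP Table 2 footnote 5 repeats this. Protocol 5.1.3: "The second study vaccination will not be administered to a subject if any of the following criteria are met"; its list includes subject refusal and investigator decision.

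**Populations.** mITT (SAP 6.3.2) needs the first vaccination and one later valid result. The PP examples (SAP 6.3.3) do not mention dose 2. In SAP Table 12, the PP Day 118 reasons include "Study Vaccination 1 Not Received" but have no counterpart for vaccination 2.

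**The concern.** The Day 90 result is a pre-dose titer only when the draw comes first and dose 2 follows. The plan permits two other courses and gives no analysis rule for either.

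- **Early dose.** If dose 2 is given at an unscheduled visit and the subject still attends Visit 6 near Day 90, the SAP takes a post-dose titer as baseline. The rise that should be measured has already happened in whole or in part.
- **No dose.** If the subject stays in follow-up and gives serum at Days 90 and 118, the change between them can be reported in PP as a response to a vaccine never received.

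What is at stake is the set of secondary estimates against the 2019/2020 strains and the serostatus subgroups in SAP Tables 71, 75 and 79. An early-dosed subject can be classed as seropositive because of dose 2 itself. For such a subject the Day 90 rows for the 2018/2019 strains also contain an effect of dose 2.

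**Working it through.** **1. The plan's own interval.** 118 − 90 = 28 days, as stated, if dose 2 is on Day 90 and the draw on Day 118. Visit 07 is not tied to the actual dose date, so even without the exceptions the permitted windows give (118 − 3) − (90 + 14) = 11 days to (118 + 3) − (90 − 14) = 45 days.

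**2. Early dose, with Visit 6 still held on Day 90.**

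| Dose 2 on | Day 90 draw is | Day 118 draw is |
|---|---|---|
| Day 60 | 90 − 60 = 30 days after dose 2 | 118 − 60 = 58 days after |
| Day 75 | 90 − 75 = 15 days after dose 2 | 118 − 75 = 43 days after |

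Both draws lie inside the PP visit windows (Days 75 to 105 and 114 to 122), so no window rule removes this subject.

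**3. Calendar.** SAP Table 14 dates first vaccinations from 17 June to 27 August 2019. Day 76 is 75 days later, between 31 August and 10 November 2019. Early dosing needs the regional trigger to be met before then. The documents do not say how often that was expected.

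**4. Size per arm (assumptions).** No rate of early or omitted dosing is given. Take N = 38 (protocol 11.4.3) and k affected subjects per arm, all kept with a fold rise of about 1 and counted as non-seroconverters. Then the observed rate is p(1 − k/38) and the observed GMFR is GMFR^(1 − k/38).

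| k of 38 | True 60% reads | True GMFR 4.0 reads |
|---|---|---|
| 1 | 58% | 3.9 |
| 2 | 57% | 3.7 |
| 4 | 54% | 3.5 |
| 8 | 47% | 3.0 |

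**5. Comparison of two arms, equal fraction f affected.** As a reference point, protocol Table 12 gives 80% power for 0.40 versus 0.72 at N = 38; enumerating the likelihood ratio test gives 0.816. The observed difference becomes 0.32(1 − f). The 2019/2020 endpoints are not tested, so power serves only as a scale.

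| f | Kept: difference | Kept: power | Excluded: n | Excluded: power |
|---|---|---|---|---|
| 2.5% | 0.312 | 0.79 | 37 | 0.80 |
| 5% | 0.304 | 0.77 | 36 | 0.79 |
| 10% | 0.288 | 0.72 | 34 | 0.78 |
| 20% | 0.256 | 0.62 | 30 | 0.73 |

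**6. Unequal omission (assumption).** With a true 50% in both arms, and 2 unadjuvanted against 6 adjuvanted subjects undosed, the rates read 0.50 × 36/38 = 47% and 0.50 × 32/38 = 42%. That is a spurious gap of about 5 points.

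**7. Other summaries.** Early-dosed subjects raise the Day 90 GMT and the percentage at 1:40 or above. Undosed subjects lower the same measures at Day 118.

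**The case against.** A reader might infer that both kinds of subject necessarily stay in the Day 118 results as false non-responders. The documents do not support that.

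- **PP retention is not certain.** SAP 6.3.3 excludes data after major deviations or events judged likely to affect immune response, and its examples are not exhaustive. SAP 7.2 reviews treatment-schedule deviations for possible exclusion, and SAP Table 6 names missed administration. This stands. But removal is discretionary, and an early dose or an omission that the protocol permits is not plainly a deviation.
- **Undosed subjects in mITT are not an error.** Keeping them is the ordinary analysis by assigned sequence. This stands, so the omission limb concerns PP only. Some 5.1.3 reasons, such as withdrawal or loss to follow-up, will usually leave no Day 118 serum.
- **The early-dose limb needs a later Visit 6 draw.** Protocol Table 3 requires blood immediately before each vaccination. If that early draw is recorded as Visit 6, the baseline is right, and a draw before Day 75 falls out of PP by the window rule. The documents do not say which course is followed. Section 8.5 lists serology among activities that may be performed and gives no order relative to the dose.
- **Not every affected subject fails to respond.** A dose shortly before the Day 90 draw may leave a measurable rise.

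A reader might also infer a bias against the adjuvanted arms. The 2-versus-6 split means 6/38 = 16% of one arm undosed, and no document supports it. Early dosing is triggered by region and randomization is stratified by site, so it should mainly dilute all arms alike. Omission of dose 2 need not be balanced, but nothing shows that it is unbalanced.

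Finally, these endpoints are secondary or exploratory, with no formal testing. That limits the stakes; it does not make a post-dose titer a baseline.

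**Conclusion.** The concern holds in limited form. Followed as written, SAP 3.2 uses a post-dose titer as baseline for any early-dosed subject whose Visit 6 draw is still taken near Day 90. That makes the 2019/2020-strain fold rise, seroconversion and serostatus wrong in mITT and, unless the discretionary clauses act, in PP. Separately, no stated PP rule and no SAP Table 12 reason prevents an undosed subject with Day 90 and Day 118 serum from entering the PP response. This is a wrong rule for a situation that the SAP itself acknowledges in footnote 5, not merely missing detail.

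The size is unknown. The illustrations assume 1 to 8 affected subjects of 38, or 2.5% to 20%, all counted as non-responders. At 2 of 38 the loss is about 3 points from a true 60%; at 8 of 38 it is about 13 points. Since the trial's stated purpose is estimation, the baseline should be pre-specified correctly even though nothing is tested.

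**What to change.** 1. **SAP 3.2.** Define the 2019/2020-strain pre-vaccination titer as the last valid serum drawn before actual dose 2, which is the unscheduled-visit serum if dose 2 was early. Set it to missing if no such serum exists. State that the Day 90 result remains the reference titer for a subject who never received dose 2.
2. **PP, 2019/2020-strain Day 118 summaries only** (seroconversion, GMFR, GMT, percentage at 1:40 or above). Require dose 2 after the baseline serum and before the Day 118 serum. Add two strain-specific reasons to SAP Table 12: vaccination 2 not received, and no serum before vaccination 2.
3. **PP Day 90 rows.** Exclude serum drawn after dose 2.
4. **Leave the rest.** Keep undosed subjects in mITT under the corrected baseline rule. Keep them in PP for the 2018/2019-strain and heterologous analyses at Days 118, 180 and 365. Those analyses use Day 1 as baseline, and undosed subjects give valid durability data there. A general requirement for dose 2 at these visits would discard such data.

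The cost is some SAP wording, two table rows and a few subjects leaving the PP 2019/2020-strain summaries. Receipt of dose 2 and its dates are already planned for reporting (SAP Tables 13 and 15, Listing 1), so no new visit or procedure is needed and no dosing rule changes.

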4. INVESTIGATIONAL PLAN

4.1. Overall Study Design and Plan

DMID Protocol 18-0011 follows a Phase I randomized, double blind study design enrolling males and non-pregnant females aged 18-45 years of age, inclusive, who are in good health as determined by medical history and physical examination, and meet all eligibility criteria, including erythrocyte sedimentation rate (ESR) and negative urine or serum pregnancy test (for females). This clinical trial is designed to assess the safety, reactogenicity and immunogenicity of either the 2018/2019 Fluzone or Flublok Quadrivalent Influenza Vaccines (QIV), manufactured by Sanofi Pasteur (SP) given without adjuvant or with one of two adjuvant formulations, AF03 (SP) or Advax-CpG55.2 (Vaxine Pty Ltd).

In this trial, subjects will be stratified by prior receipt of licensed, seasonal influenza vaccine (defined as receipt of at least one of the 2017/2018 and/or 2018/2019 influenza vaccines) and will be randomly assigned to 1 of 6 study arms to receive a single dose of one of the two seasonal 2018/2019 QIV vaccine formulations with or without one of the two adjuvants (Day 1). On approximately Day 90, each subject will receive a single dose of the seasonal 2019/2020 influenza vaccine. Treatment will be assigned to each study arm as described in [Table 1](#).

To determine early safety signals for this Phase I study, enrollment will proceed in a staged fashion for the first 6 sentinel subjects. The first six subjects will be randomized and vaccinated with one each from Groups 1-6. These six subjects will be followed through Day 8. If any of the pre-specified halting rules for the sentinel subjects occur, the study will be halted and reviewed by the DSMB. If no pre-specified safety signals are encountered enrollment will proceed.

The DSMB will review the data when the 8-day reactogenicity and clinical safety laboratory data following the first study vaccination are available for 50% of study subjects. Enrollment will not be paused for this review. An additional scheduled DSMB review will occur when all HAI, NAI and Neut data for Day 1, and Day 29 and safety data through Day 57 following the first study vaccination, are available.

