6.4. Covariates and Subgroups

This protocol defines a subgroup analysis to summarize HAI, NAI, and Neut antibody titers against vaccine strains by baseline seropositive status and previous vaccination by seasonal influenza vaccine as defined for stratification (Either 2017-2018 or 2018-2019, Neither 2017-2018 or 2018-2019). As this study is not adequately powered to perform subgroup analyses, these subgroup analyses will be used for exploratory purposes only.

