N = Number of subjects in the Modified Intent-to-Treat Population; n = Number of subjects with available results; GMT = Geometric Mean Titer ^a Ratio of GMTs is defined as the ratio of the GMT from the adjuvanted group divided by the GMT from the corresponding unadjuvanted group. Confidence intervals for the ratio of GMTs will use the Delta Method.						

Table with similar format:

Table 70: Summaries of Hemagglutination Inhibition Antibody Against 2019/2020 QIV Strains by Study Day and Study Arm, Per Protocol Population

Table 71: Summaries of Hemagglutination Inhibition Antibody Against 2019/2020 QIV Strains by Study Day, Study Arm, and Baseline Serostatus, Per Protocol Population

Time Point	Group 1 Fluzone (N=X)		Group 2 Fluzone + AF03 (N=X)		Group 3 Fluzone + Advax-CpG (N=X)		Group 4 Flublok (N=X)		Group 5 Flublok + AF03 (N=X)		Group 6 Flublok + Advax-CpG (N=X)	
	Seropositive	Seronegative	Seropositive	Seronegative	Seropositive	Seronegative	Seropositive	Seronegative	Seropositive	Seronegative	Seropositive	Seronegative
A/Brisbane/02/2018 IVR-190 (H1N1)												
Day 90 Post Vaccination 1 (Baseline)												
n	x	x	x	x	x	x	x	x	x	x	x	x
GMT (95% CI)	xxx.x (xxx.x,xxx.x)	xxx.x (xxx.x,xxx.x)	xxx.x (xxx.x,xxx.x)	xxx.x (xxx.x,xxx.x)	xxx.x (xxx.x,xxx.x)	xxx.x (xxx.x,xxx.x)	xxx.x (xxx.x,xxx.x)	xxx.x (xxx.x,xxx.x)	xxx.x (xxx.x,xxx.x)	xxx.x (xxx.x,xxx.x)	xxx.x (xxx.x,xxx.x)	xxx.x (xxx.x,xxx.x)
Ratio of GMTs (95% CI) ^a	-	-	xx.x (xx.x, xx.x)	xx.x (xx.x, xx.x)	xx.x (xx.x, xx.x)	xx.x (xx.x, xx.x)	-	-	xx.x (xx.x, xx.x)	xx.x (xx.x, xx.x)	xx.x (xx.x, xx.x)	xx.x (xx.x, xx.x)
Titer ≥ 1:40 - % (95% CI)	xx (xx, xx)	xx (xx, xx)	xx (xx, xx)	xx (xx, xx)	xx (xx, xx)	xx (xx, xx)	xx (xx, xx)	xx (xx, xx)	xx (xx, xx)	xx (xx, xx)	xx (xx, xx)	xx (xx, xx)
Day 118 Post Vaccination 1												
n	x	x	x	x	x	x	x	x	x	x	x	x
GMT (95% CI)	xxx.x (xxx.x,xxx.x)	xxx.x (xxx.x,xxx.x)	xxx.x (xxx.x,xxx.x)	xxx.x (xxx.x,xxx.x)	xxx.x (xxx.x,xxx.x)	xxx.x (xxx.x,xxx.x)	xxx.x (xxx.x,xxx.x)	xxx.x (xxx.x,xxx.x)	xxx.x (xxx.x,xxx.x)	xxx.x (xxx.x,xxx.x)	xxx.x (xxx.x,xxx.x)	xxx.x (xxx.x,xxx.x)
Ratio of GMTs (95% CI) ^a	-	-	xx.x (xx.x, xx.x)	xx.x (xx.x, xx.x)	xx.x (xx.x, xx.x)	xx.x (xx.x, xx.x)	-	-	xx.x (xx.x, xx.x)	xx.x (xx.x, xx.x)	xx.x (xx.x, xx.x)	xx.x (xx.x, xx.x)
Seroconversion - % (95% CI)	xx (xx, xx)	xx (xx, xx)	xx (xx, xx)	xx (xx, xx)	xx (xx, xx)	xx (xx, xx)	xx (xx, xx)	xx (xx, xx)	xx (xx, xx)	xx (xx, xx)	xx (xx, xx)	xx (xx, xx)

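### Tables 71, 75 and 79 give adjuvanted/unadjuvanted GMT ratios within Day 90 serostatus strata formed after randomisation, so those ratios are biased downward if the adjuvant raises Day 90 titers

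*SAP*

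**What the plan says.** Randomisation and adjuvant dosing take place on Day 1. Under SAP 4.1 subjects are "randomly assigned to 1 of 6 study arms to receive a single dose of one of the two seasonal 2018/2019 QIV vaccine formulations"; four of the six arms add an adjuvant to that dose. The same section adds: "On approximately Day 90, each subject will receive a single dose of the seasonal 2019/2020 influenza vaccine". That second dose carries no adjuvant (SAP Table 1).

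SAP 3.2 ties serostatus to the pre-vaccination titer: "Seronegative baseline status is defined as pre-vaccination antibody titer of" 1:10 or lower, and "Seropositive baseline status is defined as pre-vaccination antibody titer of" above 1:10. For the second-season strains the same section moves that titer: "However, for assay results against 2019/2020 QIV strains, pre-vaccination titer is the result obtained at Day 90".

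SAP 6.4 plans summaries "by baseline seropositive status and previous vaccination by seasonal influenza vaccine as defined for stratification" and calls them exploratory. Table 71 is titled "Summaries of Hemagglutination Inhibition Antibody Against 2019/2020 QIV Strains by Study Day, Study Arm, and Baseline Serostatus, Per Protocol Population"; Tables 75 (Neut) and 79 (NAI) follow the same pattern. All three label the Day 90 row as baseline, split each arm into seropositive and seronegative columns, and include a ratio-of-GMTs row with a 95% CI at Day 90 and Day 118.

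The outcome measures in SAP 3.1 plan titers against the 2019/2020 strains only at Days 90 and 118. A parenthesis in the matching secondary objective says Day 1, but the outcome measures beside it name Day 90 as baseline. Day 90 is therefore the natural reading of the split.

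**The concern.** A subgroup comparison between randomised arms keeps the protection of randomisation only if the subgroup is fixed before treatment. Here the subgroup is fixed about 90 days after it, by a titer that the adjuvant is intended to raise. An adjuvanted subject who is still at or below 1:10 on Day 90 failed to respond despite the adjuvant, and is a weaker responder on average than an unadjuvanted subject in the same column. The seropositive column has the matching problem: the adjuvant lifts into it people who would otherwise have been seronegative.

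At stake is the reading of the ratio rows in three tables. The plan warns only that subgroups lack power. A reader would expect wide intervals, not a systematic shift, and the word baseline hides that the strata are post-treatment.

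**Working it through.** The plan states no figure that depends on this choice, so there is none to reproduce. Three checks follow.

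**1. A bound that needs no model.** Titers below 10 are set to 5 (SAP 4.5.2) and seronegative means at most 10 (SAP 3.2). Every Day 90 value in the seronegative column lies between 5 and 10, so the Day 90 GMT ratio there must lie between 5/10 = 0.5 and 10/5 = 2.0, whatever the adjuvant does.

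**2. Size under assumed inputs.** None of these inputs is in the documents: person SD 1.6 and residual SD 0.7 (log2), unadjuvanted Day 90 GMT 40, 2-fold adjuvant effect at Day 90. Let U be the person's level. The Day 90 log2 titer is U + residual, plus 1 if adjuvanted. The Day 118 titer uses the same U with a new residual and its own arm effect.

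- SD of the Day 90 titer: √(1.6² + 0.7²) = √3.05 = 1.746.
- Reported titers are 10×2^k; taking them as rounded down, seronegative means below 20 on the underlying scale.
- Unadjuvanted cut-off: z = (log2 20 − log2 40)/1.746 = −0.573, so 28.3% are seronegative. Adjuvanted: z = (log2 20 − log2 80)/1.746 = −1.145, so 12.6%.
- Mean of U in a stratum moves by (1.6²/1.746) = 1.466 times the normal hazard term: φ/Φ below the cut-off (downward), φ/(1−Φ) above it (upward).
- Seronegative: 1.195 unadjuvanted, 1.643 adjuvanted. Difference in mean U = −1.466 × (1.643 − 1.195) = −0.657 log2, a factor of 2^−0.657 = 0.63.
- Seropositive: 0.472 unadjuvanted, 0.237 adjuvanted. Difference = −1.466 × (0.472 − 0.237) = −0.345 log2, a factor of 2^−0.345 = 0.79.

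These factors multiply the true Day 118 ratio. Simulation with 2 million subjects per arm, titers put on the SAP scale and a 2-fold rise from Day 90 to Day 118 gives nearly the same:

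| True Day 118 ratio | Seropositive | Seronegative |
|---|---|---|
| 1.00 | 0.79 | 0.66 |
| 1.41 | 1.11 | 0.90 |
| 2.00 | about 1.57 | about 1.25 |

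The small gaps from the formula in seronegatives come from setting values below 10 to 5. With a 4-fold rise the first seronegative entry is 0.64. Over unadjuvanted Day 90 GMTs of 20 to 80 and Day 90 effects of 1.4- to 2-fold, a true ratio of 1 appears as 0.72–0.92 (seropositive) and 0.61–0.85 (seronegative). With no Day 90 effect, a true ratio of 1 appears as 1.00 in both.

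**3. A different structure.** Let Day 118 depend on the Day 90 titer and on a shared tendency to respond, with Day 1 GMT about 20 and a 2-fold Day 90 effect. The overall Day 118 ratio is 1.41. The Day 90 split shows 1.02 (seronegative) and 1.17 (seropositive); a Day 1 split shows 1.41 in both. The imbalance is visible: within the Day 90 strata, Day 1 GMTs are 6.5 unadjuvanted against 5.6 adjuvanted in seronegatives, and 24.9 against 20.3 in seropositives. With a 1.5-fold effect the Day 90 split gives 1.02 and 1.09 against 1.22 overall; with 3-fold, 1.02 and 1.31 against 1.73.

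**A side effect inside the SAP.** B/Phuket and B/Maryland are in both seasons' tables. Their Day 90 and Day 118 HAI titers are split by Day 1 serostatus in Tables 39 and 40 and by Day 90 serostatus in Table 71, both under the name baseline serostatus.

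**The case against.** The other side has several good points, and most of them limit the finding.

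- **Day 90 is the right reference for the second dose.** For fold rise and seroconversion after the 2019/2020 vaccine this is correct. Serostatus just before that dose is also a fair way to describe each arm. Only the between-arm ratio fails.
- **The objective does not ask for ratios.** The outcome measures listed for the serostatus objective are the percentage with HAI titer at or above 1:40, seroconversion, GMT and GMFR. A reader might infer that this objective would be answered wrongly. The documents do not support that: all four are within-arm summaries, and the ratio row is an addition in the table shells.
- **The randomised comparison is still shown.** Tables 69/70, 73/74 and 77/78 give the second-season ratios without a split, and Tables 72, 76 and 80 split by vaccination history before randomisation. A reader might infer that a real benefit would be hidden; it would not be, for anyone who reads those tables.
- **Below 1 in both strata is not general.** A reader might infer this from the case of a true ratio of 1. That case needs a 2-fold Day 90 advantage that has vanished by Day 118. What holds across both models is a downward shift; a reversal depends on the assumptions.
- **Imprecision is large.** With 38 per arm (the protocol's Day 29 figure), the shares above give about 11 unadjuvanted and 5 adjuvanted seronegatives. Assuming a log2 SD near 1, the CI half-width is 1.96 × √(1/11 + 1/5) = 1.06 log2, a factor of about 2.1, against a bias factor of 1/0.63 = 1.6. This limits what anyone would conclude from the row, but it does not make the estimate unbiased, and the exploratory label in SAP 6.4 does not warn of bias.

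SAP 8.2 lists Tables 71, 75 and 79 among the secondary summaries while 8.3 treats them as exploratory subgroups. The secondary outcome measures themselves are defined by study group without a serostatus split, so they are unaffected either way.

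**Conclusion.** The point holds for the ratio-of-GMTs rows in Tables 71, 75 and 79, and only for them. As planned, those ratios condition on a post-randomisation titer and are shifted downward in both strata whenever the adjuvant raises Day 90 titers. Under the stated assumptions the shift is a factor of about 0.79 in seropositives and 0.63 in seronegatives, so a true 1.41 appears as about 1.11 and 0.90. An adjuvant effect persisting to Day 90 is the trial's hope, not an established fact. Without it the bias is nil, and the real size cannot be derived from the documents. Within-arm summaries by Day 90 serostatus are valid descriptions. The 2018/2019 serostatus tables, the unsplit tables and all primary and secondary outcome measures are untouched. The correction is worth making because it is cheap and the rows mislead as labelled, not because a main conclusion depends on it.

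**What to change.** Delete the ratio-of-GMTs rows from Tables 71, 75 and 79. Replace the baseline serostatus label there with one saying that the strata are defined at Day 90, after randomisation, and add a footnote that columns should not be compared between arms. Keep Day 90 as the reference for fold rise and seroconversion.

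If between-arm ratios by serostatus are wanted, add a sentence to SAP 3.2 forming those strata from the Day 1 titer:

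- B/Phuket and B/Maryland: the same strain on Day 1. First reconcile the NAI strain for the B/Victoria lineage, which is B/Colorado in Tables 56 and 60 but B/Maryland in Table 64 and Tables 77–80.
- H1N1 and H3N2: the Day 1 titer to the 2018/2019 strain of the same subtype, stated to be a proxy.

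The cost is some SAP wording and three table shells, with no new visit or blood draw. The drawback of the optional part is that, for the two A strains, serostatus is measured against a different virus, so the subgroup question changes somewhat.
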